3.5.7 Survival Follow-up – Patients who have disease progression

Once a patient experiences confirmed disease progression or starts a new anti-cancer therapy, the patient moves into the survival follow-up phase and should be contacted by telephone every 12 weeks to assess for survival status until death, withdrawal of consent, or the end of the study, whichever occurs first. If a patient progresses on treatment they will also be required to attend a SFU at 12 weeks or before the initiation of a new anti-cancer treatment; whichever comes first.

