5.0 STUDY PLAN AND PROCEDURES

5.1 Study Schedule

Whilst on this treatment patients will be assessed at the administration of the pre-loading dose and then every 3 weeks at the administration of their next dose of pembrolizumab for a total of 8 doses or until they progress, suffer unacceptable toxicities, withdraw or the study ends. After the last dose of pembrolizumab patients will be required to attend post-treatment follow-up visits as described below and/or safety follow-up (SFU) visit at 12 weeks or before the initiation of a new anti-cancer therapy, whichever comes first.

If the patient has completed all 8 doses of pembrolizumab and has not progressed or discontinued treatment for any other reason they will be seen at 4 weeks and 8 weeks after the last dose of pembrolizumab for the post treatment follow up visit. They will then return at 12 weeks for the SFU and after this be followed up every 4 weeks for 9 months or until disease progression, initiation of a new anti-cancer therapy, death, withdrawal, end of the study.

If the patient has not progressed but discontinued treatment for another reason they will be seen 8 weeks after the last dose of pembrolizumab for the post treatment follow up. They will then return at 12 weeks for the SFU and after this be followed up every 8 weeks for 9 months until disease progression, initiation of a new anti-cancer therapy, death, withdrawal or end of the study.

Patients that have progressed or initiated a new anti-cancer therapy during treatment or follow-up phase will enter into the survival follow-up phase and will be contacted every 12 weeks to assess for survival status until death, withdrawal of consent, or the end of the study, whichever occurs first. Patients that progress during treatment will be required to have a SFU at 12 weeks or before the initiation of a new anti-cancer therapy; whichever comes first.

The schedule of study assessment (Table 2) summarises the trial procedures to be performed at each visit. Individual trial procedures are described in detail below. It may be necessary to perform these procedures at unscheduled time points if deemed clinically necessary by the investigator.

Furthermore, additional evaluations/testing may be clinically indicated for reasons related to patient safety. In some cases, such evaluation/testing may be potentially sensitive in nature (e.g., HIV, Hepatitis C, etc.). Such evaluations/testing will be performed in accordance with local regulations.

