Trial Period:		Screening Phase	Treatment Cycles – Every 3 Weeks												End of Treatment - At time of discontinuation of treatment ⁴	Post-Treatment							
Treatment Cycle/Week Title:			Pre-Loading Dose	C 1	C 2	C 3	C 3	C 3	C 4	C 4	C 4	C 5	C 6	C 7		Post-Treatment Follow-up (A) ¹	Post-Treatment Follow-up (B) ²	Safety Follow-up (SFU)	Post-Safety Follow-up (A) ¹	Post-Safety Follow-up (B) ²	Survival Follow-up		
Scheduling Window (Days):				Wk 0	Wk 3	Wk 6	Wk 7 ⁸	Wk 8	Wk 9	Wk 10	Wk 11	Wk 12	Wk 15	Wk 18		4 wks and 8 wks from last dose of Pembrolizumab	8 wks from last dose of Pembrolizumab	12 wks from last dose of Pembrolizumab ³	Every 4 wks from SFU for 9 months	Every 8 wks from SFU for 9 months	Every 12 wks from progression / initiation of anti-cancer treatment		
Administrative Procedures																							
Informed Consent	X																						
Inclusion/Exclusion Criteria	X																						
Demographics, Medical & Treatment History, Smoking Status	X																						
Anti-cancer therapy Review																X	X	X	X	X			
Survival / Disease Status																X	X	X	X	X	X		
Clinical Procedures / Assessments																							
Review Adverse Events		X	X	X	X	X		X	X	X	X	X	X	X	X	X	X	X	X				
Radiation Toxicity Review				X	X			X	X	X	X	X	X	X	X	X	X	X	X	X			
Prior and Concomitant Medication Review	X	X	X	X	X			X	X	X	X	X	X	X	X	X	X	X	X				
Full Physical Exam	X																						
Directed Physical Exam		X	X	X	X	X		X	X	X	X	X	X	X	X	X			X				
Vital Signs, Weight & ECOG	X	X	X	X	X			X	X	X	X	X	X	X	X				X				
Height	X																						
Pregnancy Test – Urine/Serum	X																						
T3, T4, TSH, PT and aPTT	X			X		X			X		X		X						X				
Haematology & Biochemistry	X	X	X	X	X			X	X	X	X	X	X	X	X				X				
Urinalysis	X																						
Admin of Pembrolizumab		X	X	X	X				X			X	X	X									
Admin of Radiotherapy			X	X	X	X																	
Admin of Chemotherapy			X	X	X																		
Tumour Imaging	X													X ⁷									
Clinical disease assessment	X		X	X	X			X			X	X											
Archival collection or new tumour biopsy	X		X ⁵	X ⁵																			
HPV testing (p16 Immunohistochemistry)	X																						
Research Blood Collection (OPTIONAL)	X			X				X			X				X ⁶								
Neck dissection																							

1. For patients who have completed 8 doses of pembrolizumab and have not progressed or discontinued from unacceptable toxicities.

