5.2.4 Anti-Cancer Therapy Review

Anti-cancer therapy review will be performed at all follow-up visits as defined in the schedule of study assessment (Table 2). The investigator should review all new anti-cancer therapy initiated after the last dose of trial treatment. If a patient initiates a new anti-cancer therapy after the last dose of trial treatment, the 12 Weeks Safety Follow-up (SFU) visit must occur before the first dose of the new therapy. Once new anti-cancer therapy has been initiated the patient will move into survival follow-up.

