5.2.5 Survival / Disease Status

The investigator or qualified designee will assess the patient for survival status at specified visits as defined in the schedule of study assessment (Table 2) The assessment will include the patient status and if applicable details of patient death or details if patient has been lost to follow-up.

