5.3.9.3 Timing and Assessment of Disease

Tumour imaging may be performed by CT or magnetic resonance imaging (MRI), but the same imaging technique should be used in a patient throughout the trial. The initial tumour imaging will be performed no more than 28 days prior to confirmation of eligibility. Scans performed as part of routine clinical management are acceptable for use as the screening scan if they are of diagnostic quality and performed within the correct time window.

On-study imaging will be performed at screening then at cycle 6 to assess disease response. After cycle 6 imaging will be performed every 12 weeks for 12 months and should follow calendar days and should not be adjusted for delays in cycle starts or extension of pembrolizumab cycle frequencies.

Local investigator assessment with site radiology will be used to determine eligibility and for patient management. Tumour imaging and assessment per local standard of care should be performed for patient management, and may include additional imaging (e.g. bone scan for lung cancer patients).

Imaging should continue to be performed until documented disease progression, the start of new anti-cancer treatment, withdrawal of consent, death, or the end of the study, whichever occurs first.

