8.2.5 Data analysis

All quantitative data will be presented as number of observations, means and SDs for normally distributed data or as median and interquartile ranges for data that appear to be non-normally distributed. Qualitative data will be presented as number of observations and frequencies. When appropriate, data will be presented together with 95% confidence intervals. All statistical tests will be two-tailed and a p-value <0.05 (5%) will be considered as achieving statistical significance. The analysis will be performed separately in HPV-ve and HPV+ve cohorts, respectively.

- Baseline characteristics will be summarized using descriptive statistics. Dose limiting toxicity will be summarized using overall frequencies. Incidence (highest grade) of side effects of radiotherapy (CTCAE scale v 4.0, for acute side effects and LENT SOMA for late radiotherapy scoring systems) will be reported.
- Duration of clinical benefit will be calculated as the number of patients who had a best overall response of CR, PR, or SD according to the RECIST criteria until the first date of recurrence or progressive disease (PD) and will be measured at the landmark points in the study **6 months, 1 year and 2 years, respectively**. They will be presented as proportions and 95% confidence intervals will be reported if appropriate.
- Progression free and overall survival will be determined using Kaplan-Meier methods **presenting the median survival times, and survival rates will be reported at 6 months, 1 and 2 years, respectively**. Overall survival will be measured from date of treatment to date of death from any cause; surviving patients will be censored at date last known to be alive. Progression free survival will be measured from start of treatment to date of first appearance of disease progression, relapse or death from any cause. Patients alive without progression or relapse will be censored at date last known to be alive. Survival curves will be estimated for each HPV cohort and compared using the log-rank test.

- The levels of CD4, CD8, T regulatory cell (CD4/CD25, FOXP3), B cells, NK cells and Circulating free tumour DNA pre RT, during RT and post RT will be presented as descriptive statistics according to their HPV status. The expression of PD1 (and other immune exhaustion markers) on immune cells and PDL1 on tumour cells will be presented as descriptive statistics.

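### PFS is censored at the date last known alive, so patients who start new anti-cancer therapy without progression stay at risk after scheduled disease assessment stops, and 1-year PFS tends on average to be overstated

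*Combined protocol and SAP*

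**What the plan says.** Section 8.2.5 measures PFS from start of treatment to progression, relapse or death from any cause. For everyone else it states: "Patients alive without progression or relapse will be censored at date last known to be alive". OS has the same censoring date. Kaplan-Meier rates are reported at 6 months, 1 year and 2 years. I found no statement of how new therapy before progression is handled in PFS.

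The follow-up sections describe what happens to such a patient:

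- **Imaging (5.3.9.3).** The text reads: "Imaging should continue to be performed until documented disease progression, the start of new anti-cancer treatment, withdrawal of consent, death". That list closes with study end as a further stopping point. Footnote 7 to Table 2 also stops scans when another anti-cancer treatment starts.
- **Clinic visits (3.5.5, 3.5.6).** The 4- or 8-weekly visits that monitor disease status end when new therapy begins.
- **Contact afterwards (3.5.7).** Of a patient who switches, the section says that once he or she "starts a new anti-cancer therapy, the patient moves into the survival follow-up phase and should be contacted by telephone every 12 weeks". The stated purpose of the calls is survival status. Section 5.1 agrees: "Patients that have progressed or initiated a new anti-cancer therapy during treatment or follow-up phase will enter into the survival follow-up phase". Section 5.2.4 has the same rule: "Once new anti-cancer therapy has been initiated the patient will move into survival follow-up".
- **Content of that contact (5.2.5).** The investigator "will assess the patient for survival status at specified visits as defined in the schedule of study assessment". The details listed are patient status, death and loss to follow-up. Table 2, however, labels the row "Survival / Disease Status" and marks it at survival follow-up.

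**The concern.** A telephone call can show that a patient is alive. Without an examination or a scan it does not show that the patient is progression-free. Under the written rule the patient counts as progression-free up to the last call, although only death is reliably observed after the switch. A progression in that window is missed, or is replaced by a later death.

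The protocol foresees this path. It lists new therapy separately from progression throughout the follow-up sections, and section 6.4.1 prohibits no therapy in post-treatment follow-up.

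PFS at the three landmarks is a secondary endpoint (2.2.2, 8.2.2), and section 1.2.3 expects the study to indicate activity. The same censoring dates also enter the median PFS and the log-rank comparison of the HPV cohorts.

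**Working it through.** **Plan's own figure.** Section 8.2.4 gives the only design figure, the sample size. It reproduces: minimum 3 × 2 = 6; maximum (6 × 2 + 6) × 2 = 36, or 18 per HPV cohort. The plan states no PFS rate, event count or switching rate, so the size of the effect rests on assumptions.

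**Assumptions.** One-year PFS without switching, P = 60% or 70%, exponential. A share p = 10% or 20% of patients is assigned a switch at a time uniform on months 2-10, effective only if it precedes progression. The progression hazard after the switch is multiplied by 1, 2 or 4. Death follows progression after an exponential time of mean m = 6 or 12 months. Only death is seen after the switch, and there is no other censoring before 1 year.

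**Formula.** The overstatement at 12 months is the probability of switching, then progressing unseen, then still being alive at 12 months. With unchanged hazard, λ = −ln(P)/12 and μ = 1/m:

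p × λ/(μ−λ) × [P − e^(−12μ) × A], where A is the mean of e^((μ−λ)s) over s from 2 to 10.

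- P = 0.60, p = 0.10, m = 6: λ = 0.0426, μ = 0.1667, A = 2.19. 0.10 × 0.343 × (0.600 − 0.135 × 2.19) = 0.0104, or 1.0 point.
- P = 0.60, p = 0.20, m = 12: A = 1.28. 0.20 × 1.044 × (0.600 − 0.368 × 1.28) = 0.027, or 2.7 points.
- P = 0.70, p = 0.10, m = 6: A = 2.39. 0.10 × 0.217 × (0.700 − 0.135 × 2.39) = 0.008, or 0.8 points.

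**Range over the settings, by numerical integration (points above the true 1-year PFS):**

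| Hazard after switch | Present rule | Censoring at the switch |
|---|---|---|
| ×1 | 0.8 to 2.7 | 0 |
| ×2 | 1.5 to 4.6 | 1.1 to 2.7 |
| ×4 | 2.4 to 7.1 | 2.8 to 6.2 |

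At 6 months with unchanged hazard the present rule is 0.2 to 0.6 points too high. If half of later progressions were reported at calls, the 1-year range of 0.8-2.7 would fall to 0.4-1.3.

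**Second model.** A simulation used scans at 17, 29, 41, 53 and 65 weeks from start of treatment, 1-year PFS of 50-80%, 5-20% switching, hazard ×1 or ×2, and a mean of 40 weeks from progression to death. Compared with continued imaging, the present rule was 0.2 to 3.1 points higher at 1 year and 0.1 to 1.0 higher at 6 months. Only one scheduled scan falls before 6 months, which is why the effect is smaller there.

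**Sampling error.** 1.96 × √(0.6 × 0.4/18) = 0.226, or about 23 points.

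**Worked cohort.** Take n = 18 with 5 progressions at month 9 and 2 switchers at month 6.

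- Neither switcher has a recorded event: present rule 13/18 = 72.2%; censored before the switch 11/16 = 68.8%; new therapy as event 16/18 × 11/16 = 61.1%.
- Both switchers die at month 10: present rule 13/18 × 11/13 = 61.1%; censored 68.8%; new therapy as event 61.1%.

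**A case in the other direction.** Take n = 18 with one switcher whose unseen progression is at month 6 and death at month 11, 2 withdrawals at month 8, and 5 progressions at month 9. Full data give 17/18 × 10/15 = 63.0%. The present rule gives 11/16 × 10/11 = 62.5%, which is lower.

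**The case against.** The best defence is that following patients through new therapy to death is a recognisable treatment-policy analysis, and that the effect is small. Much of this stands.

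- **Size.** The switching rate is assumed. Section 6.4.1 bars other anti-cancer therapy during the treatment phase, so switches in the first months would require stopping trial therapy. The upper figures need 20% switching and a much higher hazard afterwards.
- **Remedy.** Censoring before the switch discards later deaths. With P = 60%, 10% switching, a four-fold hazard and 6 months to death, the true value is 56.9%, the present rule gives 59.6% and the proposed censoring 60.0%. The proposal is then the less accurate of the two.
- **Incidental capture.** The Table 2 label allows that some progressions are reported at calls. The same caution applies at the safety follow-up. Section 5.2.4 says "the 12 Weeks Safety Follow-up (SFU) visit must occur before the first dose of the new therapy", but the row marked there is the one that 5.2.5 describes as survival status. That visit does not by itself prove that a disease-assessment date exists.

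A reader might infer that the rule can only raise PFS. The last example above shows that this is false: when other patients are censored in between, a death counted late carries more weight than a progression counted on time. A reader might also infer a definite bias in 2-year PFS. The documents do not support one, because they disagree on when imaging ends.

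The defence does not remove the central gap: the plan states a censoring date that its own schedule cannot support as a progression-free date, and it does not present this as a deliberate choice.

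**Conclusion.** The point holds as a tendency. For patients who start new therapy without progression, section 8.2.5 keeps counting progression-free time after scheduled disease assessment has stopped. On average this overstates 1-year PFS, and 6-month PFS less so. Under 10-20% switching and an unchanged hazard the excess is about 1-3 points at 1 year and under 1 point at 6 months. It is larger if prognosis after switching is poor, and smaller if few switch or calls pick up progression. All of this is well inside the sampling error at n = 18. The dose taken forward is the MTD or 200 mg (3.1), so no dose decision is affected. It should be corrected because it is a stated rule for a named endpoint and the change is cheap.

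On 2-year PFS I make no numerical claim. Footnote 7 and one sentence of 5.3.9.3 schedule scans for 12 months after cycle 6. Another sentence of 5.3.9.3 continues imaging to the end of the study. Footnote 7 adds a stop at discontinuation that 5.3.9.3 does not list. Section 8.2.6 sets the secondary analysis 1 year after the last enrolment. These statements need reconciling.

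**What to change.** In section 8.2.5:

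1. Keep the date last known alive as the censoring date for OS only.
2. For PFS, censor patients alive without progression or relapse at the last disease assessment (imaging or documented clinical assessment) showing no progression. For those who start non-protocol anti-cancer therapy before progression, use the last such assessment before it starts.
3. Define which visits count as a documented clinical assessment.
4. State that this censoring may be informative.
5. Report two sensitivity analyses: new therapy as a PFS event; and the present rule, with later progressions and deaths counted and follow-up to last contact.
6. Report the number of switchers and the number at risk at each landmark.

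Separately, reconcile footnote 7 to Table 2, section 5.3.9.3 and section 8.2.6, and report 2-year PFS only where patients are still under disease assessment.

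**Cost.** A few sentences in the SAP. Scan dates are already due in the CRF (10.4), and new therapy is reviewed at follow-up visits (5.2.4). The main drawback is that the primary analysis drops events after the switch. It is therefore not a complete cure, and it can be less accurate than the present rule if prognosis after switching is poor. The two sensitivity analyses show the range.

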8.2.6 Timing of analysis

For the primary end point, the results of each dosing level will be reviewed by the safety review committee (SRC) before recruitment to the next dose level can begin and once the MTD has been determined the trial enters the expansion cohort. Analysis of the secondary endpoints will take place 1 year after the enrolment of the last patient. Analysis of the exploratory endpoints will be reported once all the relevant samples have been collected and analysed.

